#### 4.10.2.5.5 Abnormal Liver Function TEAE

Abnormal liver function TEAEs will be analyzed for the following categories.

- Abnormal liver function TEAE (defined based on the 'Drug related hepatic disorders – comprehensive search' SMQ (narrow and broad)) by SOC and PT
- TEAEs, Serious TEAEs, drug-related TEAEs, fatal TEAEs and TEAEs leading to treatment discontinuation in Hepatic Injury and Hepatic Failure FMQ (narrow) by PT
- TEAEs in Hepatic Injury and Hepatic Failure FMQ (narrow) by PT
- Patients who discontinued study treatment or post treatment follow-up due to AEs in Hepatic Injury or Hepatic Failure FDA Medical Query (FMQ) (narrow), Lab abnormality (last on treatment ALT  $\geq 2 \times$  ULN, AST  $\geq 2 \times$  ULN, ALP  $\geq 2 \times$  ULN, total bilirubin  $\geq 1.5 \times$  ULN) for patients in above categories will also be tabulated.

The number and percentage of patients experiencing events as well as the total number of reported events, classified by PT (unless otherwise specified), will be tabulated by treatment group for the following AEs of Interest.

#### 4.10.2.5.6 Local Cutaneous Reactions at the Injection Site

Local cutaneous reaction at injection site (LCRIS) is defined as (A) moderate or severe AEs with the preferred terms (PTs) including Injection site erythema, Injection site swelling, Injection site pruritus, or Injection site pain that started on the day of injection, persisted for at least 2 days (i.e., event onset date on the day of injection and resolution date not on the day of injection or the day after injection) or ongoing; or (B) any AE at the Study Drug injection site, regardless of severity, that leads to discontinuation of study drug, where AE at the Study Drug injection site is the principal reason for discontinuation.

LCRIS will be summarized by PT for each treatment group and total olezarsen treated. Patients with moderate, severe and any LCRIS will also be summarized. Discontinuations due to AE at the injection site will be summarized separately.

Percentage of injections leading to LCRIS will be summarized by PT and overall using the descriptive statistics. Additionally, percentage of injections leading to LCRIS will be summarized by moderate, severe severity and discontinuation of Study Drug due to AE at injection site.

Percentage of injections leading to LCRIS will be calculated as follows for each subject:  $(A/B) \times 100$ , where A = number of injections with an LCRIS, and B = total number of injections. Doses that are split across multiple injections are counted as a single injection.

The duration to resolution of a LCRIS and the time to onset of the first event will be summarized descriptively by treatment group and total olezarsen treated. If there are multiple LCRIS related to an injection and no overlap between events, the duration will be calculated as the sum of the duration of all LCRIS that are related to the injection. If there are overlaps, the duration will be calculated using the earliest start date and latest stop date of all LCRIS that are related to the injection. For unresolved LCRIS with missing stop date, the last participation date will be used in the calculation.

In addition, for patients who experienced LCRIS, the number of injections prior to the first LCRIS will also be summarized descriptively by treatment group and total olezarsen treated.

The LCRIS events will be provided in a listing.

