## 4.2 General Considerations

### 4.2.1 *Data Presentation*

Descriptive summary statistics including the number of subjects with non-missing data (n), mean, median, standard deviation (SD), standard error of mean (SEM), interquartile range (25th percentile, 75th percentile), and range (minimum, maximum) for continuous variables, and counts and percentages for categorical variables will be used to summarize most data. The minimum and maximum will be reported to the same number of decimal places as the raw data recorded in the database. The mean, median, lower quartile and upper quartile will be reported to one more decimal place than the raw data recorded in the database. The SD and SEM will be reported to two more decimal places than the raw data recorded in the database. In general, the maximum number of decimal places reported shall be four for any summary statistic.

Categorical data will be summarized in terms of n, frequency counts and percentages. Percentages will be rounded to one decimal place unless it is an integer. Percentages will not be presented for zero counts.

Changes from baseline in categorical data will be summarized using shift tables where appropriate.

All statistical tests will be conducted using 2-sided tests with 5% Type 1 error rates unless otherwise stated. Where appropriate, p-values will be reported. P-values greater than or equal to 0.0001, in general, will be presented to four decimal places. P-values less than 0.0001 will be presented as "< 0.0001".

Confidence intervals (CIs) will be presented to one more decimal place than the raw data.

The primary endpoint will be assessed on the Full Analysis Set (FAS) and Per Protocol Set (PPS), with the former being the basis for the primary efficacy analysis. All the secondary endpoints will be assessed on the FAS. All safety assessments will be performed on the Safety Set. PK endpoints will be assessed in the PK Set as applicable.

Efficacy and safety results will be summarized under the treatment to which patients are randomized. For safety results, should there be any cases after unblinding in which a patient received treatment other than what was randomized, such cases will be discussed and noted in footnotes where applicable.

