#### 4.10.2.5.7 Injection Site Reaction

Injection site reaction (ISR) is defined as any AE with PT or verbatim term containing 'Injection Site' that persisted for at least 2 days or ongoing. ISR will be summarized by PT for each treatment group and total olezarsen treated.

Percentage of injections leading to ISRs will be summarized by PT and overall using the descriptive statistics.

Percentage of injections leading to ISR will be calculated as follows for each patient:  $(A/B) \times 100$ , where A = number of injections with an ISR, and B = total number of injections. Doses that are split across multiple injections are counted as a single injection.

The duration to resolution of an ISR and the time to onset of the first event will be summarized descriptively by treatment group and total olezarsen treated. If there are multiple ISRs related to an injection and no overlap between ISRs, the duration will be calculated as the sum of the duration of all ISRs that are related to the injection. If there are overlaps, the duration will be calculated using the earliest start date and latest stop date of all ISRs that are related to the

injection. For unresolved ISRs with missing stop date, the last participation date will be used in the calculation.

In addition, for patients who experienced ISR, the number of injections prior to the first ISR will also be summarized descriptively by treatment group and olezarsen treated.

ISR will be listed by preferred term.

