#### 4.10.2.5.8 Flu-like Reactions

Flu-like reactions (FLRs) will also be summarized by PT for each treatment group and total olezarsen treated.

Flu-like reactions (FLR) will be evaluated using the following 2 definitions:

Definition 1 (FLR 1): defined as adverse events with PTs including Influenza like illness, Pyrexia, Feeling hot, Body temperature increased, Chills, Myalgia, or Arthralgia, starting on the day of injection or next day.

Definition 2 (FLR 2): defined as AEs with PTs including either (A) Influenza like illness or (B) Pyrexia or Feeling hot or Body temperature increased, plus at least 2 of the following symptoms with the PTs: Chills, Myalgia, or Arthralgia, starting on day of injection or the next day.

Percentage of injections leading to flu-like reactions will be summarized using the descriptive statistics.

Percentage of injections leading to flu-like reactions will be calculated as follows for each subject:  $(A/B) \times 100$ , where A = number of injections leading to flu-like reactions, and B = total number of injections.

For the subset of patients experiencing FLR(s), the time to onset of first FLR will be summarized using descriptive statistics.

FLRs will be listed by preferred term.

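### The duration summaries for injection-site reactions treat unresolved reactions as complete and count symptom-free gaps once reactions overlap; the per-patient percentages need a pooled line beside them.

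*Combined protocol and SAP*

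**What the plan says.** **Duration.** For LCRIS (SAP 4.10.2.5.6) and ISR (4.10.2.5.7), duration to resolution is summarised descriptively by treatment group. On open events the LCRIS section says: "For unresolved LCRIS with missing stop date, the last participation date will be used in the calculation". The ISR section has the same rule. Neither section plans censoring or a count of unresolved reactions.

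**Several reactions to one injection.** Both sections add up the separate durations when the reactions do not overlap. When there are overlaps, the duration runs from the earliest start to the latest stop among all reactions related to that injection.

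**Percentage of injections.** The rule appears three times: "Percentage of injections leading to LCRIS will be calculated as follows for each subject" for LCRIS, "Percentage of injections leading to ISR will be calculated as follows for each patient" for ISR and "Percentage of injections leading to flu-like reactions will be calculated as follows for each subject" for flu-like reactions (4.10.2.5.8). The ratio is (A/B) × 100, "where A = number of injections with an LCRIS, and B = total number of injections". For LCRIS, "Percentage of injections leading to LCRIS will be summarized by PT and overall using the descriptive statistics". SAP 4.2.1 lists the descriptive statistics as n, mean, median, SD, SEM, quartiles and range. No pooled per-injection rate is planned.

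**Definition of LCRIS.** One limb requires onset on the injection day. The other covers "any AE at the Study Drug injection site, regardless of severity, that leads to discontinuation of study drug", provided the reaction is the principal reason for stopping. ISR has no onset window.

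**The concern.** A reaction still open at last contact has lasted at least as long as recorded, and possibly longer. Entering the recorded time as a completed duration makes the mean and quantiles too small, most of all for persistent reactions. The rule depends on when participation ends, not on when dosing ends, so it affects completers as well as patients who leave early.

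The overlap rule changes what is measured according to an incidental feature of the records. A symptom-free gap is left out when no reactions overlap and counted when any two do.

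The mean of A/B gives a patient with one injection the same weight as a patient with 13. For LCRIS the discontinuation limb ties short exposure to having a reaction, so the mean can sit well above the share of injections that led to a reaction. A reader who takes the label literally would misread it.

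At stake is how long and how often monthly injections are said to cause local reactions in each arm. No hypothesis test is involved.

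**Working it through.** **Inputs.** Thirteen doses at Weeks 1 to 49 (protocol 8.1): (49 − 1)/4 + 1 = 13, which agrees with the stated total. Each active arm: 152 × 1/2 × 3/4 = 57 (protocol 3.1). Last scheduled visit: Day 365 + 91 = Day 456 (protocol Appendix A). The documents give no reaction counts or durations for this trial, so those below are assumptions.

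**1. Unresolved reactions.** Assume exponential durations with mean θ, onset at one of the 13 dose days (Day 1, 29, …, 337) with equal chance, and everyone followed to Day 456. Available follow-up C is 456 minus the onset day, from 455 down to 119 days. The share unresolved is the average of exp(−C/θ), and the mean under the SAP rule is θ × (1 − share unresolved).

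| Assumed mean (days) | Unresolved | Recorded mean (days) |
|---|---|---|
| 60 | 2.8% | 58 |
| 180 | 24% | 137 |
| 365 | 47% | 192 |

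Under this model the relative bias equals the share unresolved. Nobody leaves early in this calculation, so the bias arises in completers alone; early leavers with open reactions would add to it.

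A small example for short reactions and early leavers: eight resolve at 3, 4, 5, 6, 8, 10, 14 and 20 days, and two are unresolved when last seen at days 3 and 4.
- SAP rule: the sorted times are 3, 3, 4, 4, 5, 6, 8, 10, 14, 20, so the median is (5 + 6)/2 = 5.5 days.
- Kaplan-Meier: 9/10 × 7/8 × 5/6 × 4/5 = 0.525 after day 6, then × 3/4 = 0.394 at day 8, so the median is 8 days.

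**2. Overlap rule, counting days inclusively.** Take three ISRs related to one injection.
- Days 0–3, 2–5 and 20–22: two overlap, so the SAP duration is Day 0 to Day 22 = 23 days. Days with a reaction are 6 + 3 = 9.
- Days 0–2, 3–5 and 20–22: the same nine days, no overlap, so the SAP duration is 3 + 3 + 3 = 9 days.

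SAP 4.10.2.1 makes the trigger unclear. A change in severity creates a second record that starts on the date the first one stops, and the SAP does not say whether a shared date is an overlap.

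**3. Mean of A/B against ΣA/ΣB, arm of 57.**
- One patient with 1 of 1, five with 1 of 13, 51 with 0 of 13: mean (100 + 5 × 100/13)/57 = 2.43%; pooled 6/(56 × 13 + 1) = 6/729 = 0.82%.
- Two with 1 of 1, four with 1 of 13, 51 with 0 of 13: mean (200 + 4 × 100/13)/57 = 4.05%; pooled 6/(55 × 13 + 2) = 6/717 = 0.84%.
- Opposite case, 11 with 0 of 1 and 46 with 1 of 13: mean (46 × 100/13)/57 = 6.2%; pooled 46/(46 × 13 + 11) = 46/609 = 7.6%.

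The gap can go either way, depending on whether those who stop early had reactions. In the first two cases only 6 of 57 patients had any reaction, so the median is 0 under the SAP.

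**The case against.** **The per-patient ratio is openly defined.** The SAP says it is calculated for each subject and reports the median, quartiles and range as well as the mean. A patient-weighted mean and an injection-weighted ratio answer different questions, and the pooled ratio gives most weight to patients who tolerated all 13 doses. This stands: the pooled ratio belongs beside the planned mean and is not the one correct figure. A reader might infer that every one-injection stopper counts as 100%, or that frequency is overstated in any arm with early stoppers. Neither follows: a stopper without a reaction enters as 0% and pulls the mean down.

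**Unresolved reactions are not recoded as resolved.** The last participation date enters only the duration calculation. AE outcomes are unchanged, and AE listings keep the reported dates (SAP 4.10.2.2). This stands.

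**Patients who stop drug are still followed.** Protocol 8.7.1 asks for a visit 4 weeks after the last dose and then 13 weeks of follow-up, so a patient who stops after Day 1 and completes it is observed for about 28 + 91 = 119 days. The tempting reading that frequency is overstated and duration understated for the same patients is therefore not supported. Duration is understated only when participation ends with a reaction still open.

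**The large duration biases need reactions lasting months.** No figure in the documents supports such durations, and protocol 2.3.4 describes injection site reactions in the earlier Phase 2 study as predominantly mild. This limits the likely size but does not make the rule sound.

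**The gap example needs a particular pattern.** It takes at least three reactions to one injection, with two overlapping and one separate. It cannot arise among LCRIS that all start on the injection day. It remains possible for ISR and, in principle, for LCRIS that qualify through discontinuation.

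**Conclusion.** The point holds as a minor one. The duration rule mixes censored and completed times, so any bias is downward. It is negligible for short reactions (under 3% at an assumed mean of 60 days) and substantial for persistent ones (137 days recorded at an assumed mean of 180). These sizes rest on exponential durations, uniformly distributed onset and full follow-up to Day 456. The overlap rule is internally inconsistent whatever its frequency, and that frequency cannot be judged from the documents. The unweighted mean of A/B is a legitimate summary but not the share of injections with a reaction; the gap can be large in either direction.

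The documents do not support going further and saying that these are the main tolerability figures or that the safety comparison between arms is distorted. The SAP separately plans patient counts and event totals, patients with moderate, severe and any LCRIS, discontinuations due to injection-site events, and listings. None of these uses A/B or the end-date rule.

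**What to change.** 1. **SAP 4.10.2.5.6 and 4.10.2.5.7, duration.** Analyse time to resolution with unresolved reactions censored at the last participation date. Report the Kaplan-Meier median and the number unresolved per arm. The AE form already has an outcome for events that persist (protocol 9.4.3.5), so the censoring flag exists.
2. **Same sections, several reactions to one injection.** Report reaction days per injection separately, as the number of days covered by at least one reaction, and flag injections with a reaction still open. State how records that share a date after a severity change are joined. Keep this apart from time to resolution, because the two measure different things.
3. **SAP 4.10.2.5.6 to 4.10.2.5.8, percentage of injections.** Keep the per-patient distribution and add ΣA/ΣB per arm as a supplementary line. This matches the SAP's own exposure-adjusted event rate in 4.2.1, which divides total events by total duration.

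The cost is SAP wording and a few lines of code, with no new data.

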#### 4.10.2.5.7 Injection Site Reaction

Injection site reaction (ISR) is defined as any AE with PT or verbatim term containing 'Injection Site' that persisted for at least 2 days or ongoing. ISR will be summarized by PT for each treatment group and total olezarsen treated.

Percentage of injections leading to ISRs will be summarized by PT and overall using the descriptive statistics.

Percentage of injections leading to ISR will be calculated as follows for each patient:  $(A/B) \times 100$ , where A = number of injections with an ISR, and B = total number of injections. Doses that are split across multiple injections are counted as a single injection.

The duration to resolution of an ISR and the time to onset of the first event will be summarized descriptively by treatment group and total olezarsen treated. If there are multiple ISRs related to an injection and no overlap between ISRs, the duration will be calculated as the sum of the duration of all ISRs that are related to the injection. If there are overlaps, the duration will be calculated using the earliest start date and latest stop date of all ISRs that are related to the

injection. For unresolved ISRs with missing stop date, the last participation date will be used in the calculation.

In addition, for patients who experienced ISR, the number of injections prior to the first ISR will also be summarized descriptively by treatment group and olezarsen treated.

ISR will be listed by preferred term.

#### 4.10.2.5.8 Flu-like Reactions

Flu-like reactions (FLRs) will also be summarized by PT for each treatment group and total olezarsen treated.

Flu-like reactions (FLR) will be evaluated using the following 2 definitions:

Definition 1 (FLR 1): defined as adverse events with PTs including Influenza like illness, Pyrexia, Feeling hot, Body temperature increased, Chills, Myalgia, or Arthralgia, starting on the day of injection or next day.

Definition 2 (FLR 2): defined as AEs with PTs including either (A) Influenza like illness or (B) Pyrexia or Feeling hot or Body temperature increased, plus at least 2 of the following symptoms with the PTs: Chills, Myalgia, or Arthralgia, starting on day of injection or the next day.

Percentage of injections leading to flu-like reactions will be summarized using the descriptive statistics.

Percentage of injections leading to flu-like reactions will be calculated as follows for each subject:  $(A/B) \times 100$ , where A = number of injections leading to flu-like reactions, and B = total number of injections.

For the subset of patients experiencing FLR(s), the time to onset of first FLR will be summarized using descriptive statistics.

FLRs will be listed by preferred term.

#### 4.10.3 Clinical Laboratory Evaluation

##### 4.10.3.1 General Analysis of Safety Laboratory Data

The following is the list of routine lab analytes that will be collected throughout the study:

- **Clinical Chemistry:** Sodium, Potassium, Chloride, Bicarbonate, Total Protein, Albumin, Calcium, Magnesium, Phosphorus, Glucose, Blood Urea Nitrogen (BUN), Creatinine, Uric Acid, Total bilirubin, Direct (conjugated) bilirubin, Indirect (unconjugated) bilirubin, Alanine aminotransferase (ALT), Aspartate aminotransferase (AST), Alkaline phosphatase (ALP), Creatinine kinase (CK), and Gamma-glutamyl transferase (GGT)
- **Hematology:** Red blood cells, Hemoglobin, Hematocrit, Mean corpuscular volume (MCV), Mean corpuscular hemoglobin (MCH), Mean corpuscular hemoglobin concentration (MCHC), Red cell distribution width (RDW), Platelets (PLTs), Mean platelet volume (MPV), White blood cells (WBCs), and WBC differential (percentage and absolute) (Neutrophils, Eosinophils, Basophils, Lymphocytes, and Monocytes)
- **Coagulation:** activated partial thromboplastin time (aPTT), prothrombin time, international normalized ratio (INR)
- **Other assessments:** Hemoglobin A1C (HbA1c)

- **Screening Tests:** Hepatitis B surface antigen, Hepatitis C antibody, HIV antibody, FSH (for confirmation of menopause at Screening per inclusion criteria), Serum  $\beta$ hCG (only women who are not surgically sterile or post-menopausal). The screening test data will only be displayed in patient listings.
- **Urinalysis:** Color, Appearance, Specific gravity, pH, Protein, Blood, Glucose, Ketones, Bilirubin, Urobilinogen, Leukocyte esterase, Nitrate, Microscopic examination, Urinary protein/creatinine (UPCR) ratio, Urine albumin/creatinine ratio (UACR). The expanded urinalysis data will be only displayed in patient listings. Urine albumin/creatinine ratio (a/c ratio) and protein/creatinine ratio (p/c ratio) will be summarized.
- **Inflammation:** CRP measured by high sensitivity assay (hsCRP)

If the quantitative data were reported as "< X", i.e., below the lower limit of quantification, or "> X", i.e., above the upper limit of quantification, will be converted to X for the purpose of quantitative summaries/figures, but will be presented as recorded (i.e., "< X" or "> X") in the listings.

The following clinical laboratory summaries will be provided by treatment group and total olezarsen treated.

- Quantitative assessments will be summarized using descriptive statistics in terms of observed values, change and percent change from Baseline for each laboratory parameter by scheduled study visit.
- Qualitative assessments will be summarized by frequency counts and percentages by scheduled study visit.

By-subject listings of all laboratory data will be provided based on randomized patients.

#### *4.10.3.2 Additional Analyses of Key Safety Abnormal Laboratory Data*

The following categories of key safety laboratory data will be evaluated over the whole post-baseline period. The number and percent of patients with post-baseline results falling in each category below will be tabulated by treatment group and total olezarsen treated. Percentage is calculated using the number of subjects with at least one post-baseline result meet the specific criteria listed below as numerator and the number of subjects with at least one non-missing post-baseline value as denominator. The risk differences and corresponding 95% CIs between each active treatment group (total olezarsen treated) and pooled placebo group will be provided for the selected categories. Results with visit labels as "Unscheduled" will be included in the abnormality summary.

